3.2. Rationale for Overall Study Design

The overall study design is commonly used for Phase 1 safety and PK studies. Incorporation of sentinel subjects in any cohort, especially the first cohort, is designed to limit the number of subjects exposed to a potentially unsafe drug or unsafe dose. The durations of the in-clinic stays are based on safety and practical considerations to ensure proper assessment of potential AEs and collection of biological samples and various examinations/measurements required by the study. An EOS or EOE Visit is conducted at 28 days after the last dose to assess the outcome of AEs (if any) after study drug treatment and to ensure proper reporting of AEs with onset during the post-treatment period. Use of an SRC to assess safety and PK data before dose escalation and before transitioning from single doses (Part A) to multiple doses (Parts B and C) is standard practice in such studies. Having safety and PK data in healthy subjects before dosing subjects with the proposed indication(s) (Parts D, E, and D Extension) is also standard practice. Having longer duration doses not exceed doses that have been studied for shorter durations is standard practice as well. Having the Investigator (with explicit agreement from the Sponsor) rather than the SRC decide if safety for the sentinel subjects in Cohort A1 is acceptable and if a subject in Part D or E will start multiple dosing with study drug after the single dose are practical consideration because the decisions needs to be made within 24 hours (Cohort A1) and within the 5-day washout period (individual subjects in Parts D and E). Galactose and its metabolites are only measured in subjects with CG or GALK-deficient Galactosemia (Parts D, E, and D Extension) because AR (the enzyme inhibited by AT-007) converts galactose to galactitol only in the presence of extremely high levels of galactose (found in subjects with CG or GALK-deficient Galactosemia but not healthy subjects).

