Three dosing cohorts are planned for subjects with CG (Part D). The same subjects will receive both the single dose and the multiple doses. Within each cohort of 6 subjects, 4 subjects will be randomly assigned to AT-007 and 2 subjects will be randomly assigned to placebo. Following a single dose of study drug (AT-007 or placebo), there will be a 5-day washout. Subjects who tolerate the single-dose will receive 1 daily dose of the same study drug (AT-007 or placebo) for 27 consecutive days. The decision of whether each individual subject can start multiple dosing

will be made by the Investigator in consultation with the Sponsor. **No subject in Part D can start multiple dosing without explicit agreement from the Sponsor.** Subjects will complete the 27 days of treatment and the associated PK, PD, and safety assessments through the 2 days after the MAD portion and then have an EOS Visit at 28 days after the last dose.

The starting dose for Part D (i.e., for Cohort D1) was based on results from Part A (Cohorts A1 through A4) and Cohorts B1 and B2 and at 5 mg/kg was lower than the dose for Cohort B2 (10 mg/kg). The dose for Cohort D2 (20 mg/kg) was based on results from these cohorts plus Cohorts B3 and D1; results for Cohort C1 were also considered. The dose for Cohort D3 will be based on results from all cohorts in Parts A and B and Cohorts D1 and D2 and will not be higher than the dose for Cohort B4.

Before the study proceeds to Part E (SAD and MAD in subjects with GALK-deficient Galactosemia), safety data from all completed cohorts in Parts A, B, and D of the study will be evaluated by the SRC and all PK data from these cohorts will be evaluated by the Sponsor. The starting dose for Part E will not be higher than the highest acceptable dose in Part D at the time of starting Part E (after all subjects complete Cohorts D1 and D2 but may be before, during, or after Cohort D3). The dose for subsequent cohorts (if any) in Part E will be based on results from the previous cohort(s) in Part E.

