One to 3 dosing cohort are planned for subjects with GALK-deficient Galactosemia (Part E). The same subjects will receive both the single dose and the multiple doses. Within each cohort of 6 subjects, 4 subjects will be randomly assigned to AT-007 and 2 subjects will be randomly assigned to placebo. Following a single dose of study drug (AT-007 or placebo), there will be a 5-day washout. Subjects who tolerate the single-dose will receive 1 daily dose of the same study drug (AT-007 or placebo) for 27 consecutive days. The decision of whether each individual subject can start multiple dosing will be made by the Investigator in consultation with the Sponsor. **No subject in Part E can start multiple dosing without explicit agreement from the Sponsor.** Subjects will complete the 27 days of treatment and the associated PK, PD, and safety assessments through the 2 days after the MAD portion and then have an EOS Visit at 28 days after the last dose.

Notes for Parts D and E: The overall number of subjects per cohort may be increased up to 8 subjects to address any potential lost-to-follow-up among subjects treated with either placebo or AT-007. Subjects treated with study drug (placebo or AT-007) in a cohort may be randomized to treatment in another cohort (separate consent required) within the same Part (assuming no safety or tolerability issues in the prior cohort) as long as there is a washout period of ≥ 5 days between the last dose in a cohort and the first dose in the next cohort.

The dose for the first cohort of the Part D Extension (DE1) will be 20 mg/kg/day based on acceptable SAD and MAD safety and PK data from Cohort D2. After SRC review of all SAD and MAD data and Sponsor review of PK and galactitol data for Cohorts D1 through D3, a second cohort of the Part D Extension (DE2) may be initiated to evaluate a dose >20 mg/kg/day if this dose was well tolerated in the SAD and MAD portions of the study in both healthy volunteers and subjects with CG.

In Part D Extension, within each cohort of up to 28 subjects, subjects will be randomly assigned in a 3:1 to AT-007 and placebo. Subjects will receive 1 daily dose of the same study drug (AT-007 or placebo) for 90 consecutive days. Subjects will complete the 90 days of treatment

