The SRC will make recommendations to the Sponsor regarding dose escalation or de-escalation for each cohort based on the results from the previous cohort as described in [Section 3.4](#). The Sponsor will act upon this recommendation and inform the Investigator(s) and the IRB(s)/IEC(s).

The SRC will pay particular attention to DLTs defined as any AT-007-related AE or clinically relevant finding on laboratory tests, ECGs, vital signs, or physical examinations that, in the opinion of the Investigator and/or the SRC, precludes administering the dose to any subject and/or continuing to administer daily doses to the subject who experienced the event. Specific individual subject-level dose stopping criteria for hepatic and renal toxicity are described in [Appendix G](#) and [Appendix H](#). For DLTs, as well as fatal serious adverse events (SAEs) and life-threatening SAEs, breaking the blind will be considered and initiated (as needed) per SRC discussion and agreement.

Dose-escalation will be stopped and de-escalation initiated if:

- ≥ 2 subjects on AT-007 (B and C cohorts of the same dose level considered together) experience a DLT at any time through 24 hours after the last dose of study treatment
- Any subject on AT-007 has a fatal SAE or life-threatening SAE requiring urgent intervention at any time through 24 hours of the last dose of study treatment

The maximum tolerated dose (MTD) will be the dose level below the dose level at which one or more of the events listed above occurs.

Dose escalation within each part of the study will continue until the MTD is identified per the rules described earlier in this section or the SRC and/or Sponsor decide to stop dose escalation. Dose de-escalation, if initiated within any part of the study, will continue until the MTD is identified or the SRC and/or Sponsor decide to stop.

If the events outlined in the above MTD definition do not occur at any dose level in a study part, then the MTD will be the highest dose level in that study part.

If the events outlined in the above MTD definition occur at any given dose level, the Sponsor may decide to investigate a dose higher than the previously well-tolerated dose but lower than the dose at which one of the events outlined in the above MTD definition occurred.

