6.7.2. Non-dosing Days Between Single and Multiple Dosing (Days 2 through 5)

Between the single and multiple dosing periods in Part D, there is a 5-day washout period that starts immediately after the Day 1 dose and ends immediately before the Day 6 dose (first dose of the multiple dosing period).

6.7.2.1. Day 2

Subjects will remain in the CRU on Day 2.

The following procedures will be done on Day 2:

- Finish collecting postdose urine through 24 hours after the dose for analysis of galactitol (an aliquot of the total urine collected will be analyzed for creatinine)
- For Cohort D3 only, collect postdose urine for PK
- Collect postdose blood samples for PK
- Collect postdose blood samples for analysis of biomarkers of galactose metabolism including galactose, galactitol, and galactose-1-p

- Measure vital signs
- Collect AE and concomitant medications data
- Feed the subject (3 meals)

Note: Blood collection for PK and biomarkers (and urine collection for PK for Cohort D3 only) will continue into Day 3.

6.7.2.2. Day 3

Subjects in Cohort D3 only will remain in the CRU on Day 3. Subjects in Cohorts D1 and D2 and Part E will be discharged on Day 3.

The following procedures will be done on Day 3:

- For Cohort D3 only, collect postdose urine for PK
- Collect postdose blood sample for PK
- Collect postdose blood sample for analysis of biomarkers of galactose metabolism including galactose, galactitol, and galactose-1-p
- Measure vital signs
- Collect AE and concomitant medications data
- Discharge subject (Cohorts D1 and D2 and Part E only) from the CRU with a reminder to return on the morning of Day 6 after an overnight fast of at least 10 hours
- Feed the subject (3 meals) (Cohort D3 only)

Note: For Cohort D3 only, urine collection for PK will continue into Day 4.

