6.7.3. Day 6 (First Study Drug Dosing Day for Multiple Dosing Period)

Subjects will arrive in the morning (preferably in time for pre-dose procedures and 8 am dosing).

The following procedures will be done before study drug administration on Day 6:

- Perform physical examination including weight
- Measure predose vital signs
- Conduct predose 12-lead ECG

- Collect fasting blood sample(s) for clinical laboratory testing (hematology, coagulation and biochemistry)
- Collect fasting urine sample for urinalysis and, for female subjects of childbearing potential only, urine pregnancy test (pregnancy test must be negative for the subject to receive study drug)

Then, study drug (AT-007 or placebo) will be administered to the subject, and the following procedures will be done on Day 6 after the dose:

- Conduct postdose 12-lead ECG
- Measure postdose vital signs
- Feed the subject (breakfast provided at ≥ 2 hours postdose)
- Dispense study drug for Days 7 through 11
- Remind the subject/caregiver that study drug should be taken QD under fasting conditions at approximately the same time of day as on Day 6 and to record the date/time of each dose on the study drug diary card ([Section 5.3](#))
- Remind the subject/caregiver to fast overnight for at least 10 hours and return to the CRU (before either taking study drug or breaking the fast) on the morning of Day 12

Adverse event and concomitant medication data will be collected both before and after dose administration on Day 6.

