APPENDIX H. GUIDANCE IN CASE OF WORSENING RENAL FUNCTION

Renal function must be closely monitored during the study, particularly during administration of potentially nephrotoxic drugs, such as acetaminophen, non-steroidal anti-inflammatory drugs (NSAIDs), fluoxetine, antihistamines, antimicrobials, benzodiazepines, proton pump inhibitors, phenytoin, trimethoprim, fenofibrate, cimetidine, cephalosporins, probenecid, aminoglycoside, amphotericin, ketoconazole, and clofibrate

Urine protein-to-creatinine ratio (UPCR), urine albumin-to- creatinine ratio (UACR) and eGFR will be assessed at each visit. In case of increased UPCR (≥ 200 mg/g), increased UACR (≥ 30 mg/g), eGFR < 30 mL/min/1.73 m², or decreased eGFR $> 30\%$ compared to baseline, a retest must be performed within 24 hours and if the abnormal laboratory result is confirmed, the following actions will be taken:

- The event must be reported to the Sponsor within 24 hours
- Concomitant medications will be reviewed and any potentially nephrotoxic drug must be discontinued
- Recent medical history will be investigated specifically for significant increase or decrease of blood pressure, plasma volume depletion, flu-like symptoms, urinary tract infection, and abdominal pain suggestive of obstructive uropathy.
- If there is no suspected concomitant medication , or if no improvement of renal function is observed after 72 hours of discontinuation of the potentially nephrotoxic drug, and if there is nothing in recent medical history that is likely to cause the abnormal renal function, the study drug will be temporarily discontinued.
- The following urinary markers of kidney injury must be measured: Clusterin (CLU), Cystatin-C (CysC), Kidney Injury Molecule-1 (KIM-1), N-acetyl-beta-D-glucosaminidase (NAG), Neutrophil gelatinase-associated lipocalin (NGAL), and Osteopontin (OPN)
- A renal ultrasound will be performed.
- A nephrologist will be consulted
- Renal function (eGFR, UPCR and UACR) will continue to be monitored every 48 hours until stabilization, then every 2 weeks until normalization.
- At this time, the Investigator in consultation with the nephrologist will decide if the study drug may resume

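### Parts D and E: no hematology, chemistry, coagulation or urinalysis result is required after the single dose and before the first of 27 daily doses

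*Protocol*

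**What the plan says.** **The gate.** Protocol Section 3.1 states "No subject in Part D can start multiple dosing without explicit agreement from the Sponsor" and, for the other patient part, "No subject in Part E can start multiple dosing without explicit agreement from the Sponsor". Sections 3.3.4 and 3.3.5 limit multiple dosing to subjects who tolerated the single dose. They name no data on which that judgement must rest. Section 3.2 explains why the Investigator, with Sponsor agreement, decides instead of the Safety Review Committee: "the decisions needs to be made within 24 hours (Cohort A1) and within the 5-day washout period (individual subjects in Parts D and E"). Section 6.7.2 fixes the window: "there is a 5-day washout period that starts immediately after the Day 1 dose and ends immediately before the Day 6 dose".

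**The lab schedule.** Sections 6.7.1 and 6.7.2 list PK and biomarker sampling, urine collection, vital signs, adverse events and concomitant medications after the Day 1 dose, with one postdose ECG on Day 1. They list no safety labs. The laboratory rows of Appendices D and E go from Screening/Day -1 to Day 6. SAP Section 3.2.2 gives the same days for both parts: Screening, -1, 6, 12, 20, 32 and EOS.

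**Day 6.** Section 6.7.3 places this item in the predose block: "Collect fasting blood sample(s) for clinical laboratory testing (hematology, coagulation and biochemistry"), together with urinalysis. One result is tied to dosing, for women of childbearing potential: "pregnancy test must be negative for the subject to receive study drug". The introduction to Section 6 allows fasting safety samples to be drawn after the dose, provided the fast is unbroken. Section 10.5 allows a local or central laboratory for these tests and gives no turnaround time.

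**The concern.** This gate is the individual patient's safeguard between one dose and repeat dosing, most of it at home. The protocol treats laboratory findings as part of tolerability. Section 3.5 has "DLTs defined as any AT-007-related AE or clinically relevant finding on laboratory tests, ECGs, vital signs, or physical examinations", where the finding precludes, among other things, further daily doses in that subject. The subject-level rules in Appendices G and H act on ALT, AST, bilirubin, eGFR, UPCR and UACR. Early changes in these values may not show in vital signs or reported symptoms.

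A team that follows the schedule exactly can agree to multiple dosing with none of these values in hand after the single dose. Once the Day 6 results arrive, the two appendices apply. What is at stake is the doses taken before then.

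**Working it through.** **1. The plan's own figures.** Washout: 6 - 1 = 5 days. Multiple dosing, Day 6 to Day 32 inclusive: 32 - 6 + 1 = 27 doses. Both agree with Sections 3.3.4 and 3.3.5.

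**2. Lab sets between the two dosing periods** (Sections 6.4.2 and 6.7.1 to 6.7.3, Appendices D and E, SAP 3.2.2).

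| | Part A | Part D | Part E |
|---|---|---|---|
| Safety lab sets after the single dose and before Day 6 | 1 (Day 3) | 0 | 0 |
| Safety lab sets at the Day 6 visit, listed predose | not applicable | 1 | 1 |
| Hematology, chemistry, coagulation or urinalysis results required before the first multiple dose | not applicable | 0 | 0 |

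The creatinine measured in the Day 1 to 2 urine is an aliquot of the galactitol collection. It is not a safety lab.

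**3. Does Appendix H fill the gap?** It says UPCR, UACR "and eGFR will be assessed at each visit". Section 6.7 and Appendices D and E schedule no such collection on Days 1 to 5. The sentence does not cover liver tests or hematology, and it does not make a result a condition of starting. Section 6.10 permits extra tests at the Investigator's judgement but does not require them.

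**4. Doses taken before the Day 6 results.** Put the Day 6 draw and dose at t = 0, with daily doses at 0, 24, 48, ... h. Turnaround T is an assumption, because the documents do not state it.

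| Results return | Doses already taken |
|---|---|
| Before dosing that morning | 0 |
| After dosing, up to 24 h | 1 |
| 24 to 48 h | 2 |
| 48 to 72 h | 3 |

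**5. Doses before the next scheduled draw.** Section 6.7.4 lists the Day 12 safety labs after that day's dose: Days 6 to 12, 12 - 6 + 1 = 7 doses. If the team draws them predose, as the Section 6 introduction permits: Days 6 to 11, 6 doses.

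**6. What a Day 3 draw would give.** The 48-h sample falls 48 h after the Day 1 dose and the Day 6 dose at 5 × 24 = 120 h, leaving 120 - 48 = 72 h. With the ±1-day visit window on Day 6 (96 to 144 h), the margin is 48 to 96 h. At nominal timing, no multiple dose precedes a result with turnaround up to 72 h; if Day 6 comes a day early, up to 48 h.

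**7. Reach.**
- Part E has 1 to 3 cohorts of 6 (4 active, 2 placebo): 6 to 18 entries, 4 to 12 on AT-007.
- Cohort D3, if still open, adds 6 entries, 4 on AT-007.
- Together: 12 to 24 entries, 8 to 16 on AT-007.
- If all are already dosed: 0.

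**The case against.** **Looser timing elsewhere.** The strongest argument is that the same protocol accepts later first labs under repeat dosing. Parts B and C dose daily from Day 1, with the first on-drug labs on Day 6, after five doses. The Part D Extension takes de novo patients straight to daily 20 mg/kg, with the first on-drug labs on Day 30. Against that, one to three doses before a result looks modest. This stands as a reason to rate the point low. It does not remove the point, because those parts have no individual decision between a single dose and multiple dosing. Parts D and E do, and that decision lacks the data it would naturally use.

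**The Day 6 draw lies inside the window.** It is listed predose, unlike the Day 12, 20 and 32 labs, and a local laboratory may be used. Teams may wait for the result, and nothing stops them. That is fair, but nothing asks them to wait either, Section 6 lets the draw follow the dose, and dosing is preferred at about 8 am.

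**Other safeguards.** The Safety Review Committee sees labs through Day 12 for each cohort, Cohort B4 is reviewed before D3, the Part E dose is capped by Part D, and the unblinded Sponsor follows PK and galactitol. These bear on dose level and exposure. None supplies this patient's own liver, renal or hematology result before repeat dosing.

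**Stronger readings that do not hold.** A reader might infer that no laboratory result at all is needed on Day 6. That is wrong: the pregnancy test must be negative, and Section 7.1.2 lists it among the clinical laboratory tests. It says nothing about tolerance of the single dose, however. A reader might also take 12 to 24 entries as the number affected. The note leaving the D3 dose open dates from protocol version 5.0, the SAP already cites version 6.0, and Section 5.3 uses the past tense for study drug in Parts D and E. That wording does not prove dosing is complete, but it rules out leading with the larger figure.

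**Conclusion.** The gap is real and minor. The visit text, both appendices and the SAP agree that no hematology, chemistry, coagulation or urinalysis is scheduled between the single dose and the Day 6 visit. No text requires the Day 6 results before the first of the 27 doses. The decision that a patient tolerated the single dose can therefore be made without any post-dose liver, renal or hematology value.

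The size is 1 to 3 doses before results, assuming they return after dosing and within 72 h, and none if they return the same morning before dosing. The next scheduled draw follows 7 doses as written, or 6 if taken predose. Reach is limited to cohorts not yet dosed and may be zero; the Sponsor should confirm the status of D3 and Part E. The documents do not show that any team has dosed without looking at labs, only that the plan allows it.

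**What to change.** - Add the fasting safety set (hematology, chemistry, coagulation, urinalysis) to the existing 48-h in-clinic draw on Day 3 in Section 6.7.2.2, Appendices D and E and SAP 3.2.2, as Part A does, with an overnight fast on Day 2.
- State in Sections 3.3.4 and 3.3.5, and in the matching SAP Sections 3.1.4.4 and 3.1.4.5, that the Investigator and Sponsor review these results before agreeing to multiple dosing. How the results bear on starting stays their decision.
- Keep the Day 6 predose draw, which can catch changes arising after 48 h.

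The minimum alternative is one sentence requiring review of the Day 6 results before the Day 6 dose. It works without delaying the dose only where results return the same morning.

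The cost is protocol and SAP wording plus one routine set of tubes and one urine sample per subject, with no extra visit. The downside is slightly more blood and one more fast. In Cohort D3 the urinalysis sample falls within the 72-h PK urine collection, so its volume must be recorded; Cohorts A4 and A5 had the same overlap on Day 3.

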3.3. Study Drug Administration Schedules

Parts A, B, C, and D of the study will start more or less sequentially followed by starting Parts E and D Extension more or less concurrently. However, conduct of all study parts will overlap ([Figure 2](#) and [Section 3.1](#)).

Within each multi-cohort part, the cohorts (dose levels) will be dosed sequentially. The SRC will review available safety data through a pre-specified timeframe (Day 3 for Part A, Day 8 for Parts B and C, and Day 12 for Part D [and E, if applicable]) and provide recommendations for the next cohort. If there is a second cohort in Part D Extension, the dose will be higher than

20 mg/kg and depend on the results for that dose in healthy subjects and subjects with CG in Part D. Additional cohorts will be enrolled if it is deemed appropriate after safety assessment by the SRC and confirmation by the Sponsor. A decision to repeat a dose level or to study another higher or lower dose level may be made. The Investigator(s) and Institutional Review Boards (IRBs) / Independent Ethics Committees (IECs) will be notified of these decisions.

The SRC will also review data for the last cohort for each study part except that there will be no next cohort within the same part of the study.

AT-007 dose levels in Part A were between 0.5 and 40 mg/kg. Dose levels in subsequent parts of the study are based on the safety and PK results (and galactitol results in Parts D, E, and E Extension only) of previous cohorts and/or previous parts of the study. Doses higher than 40 mg/kg may be evaluated if the human C_{max} and AUC are substantially lower than the corresponding values calculated in nonclinical experiments and no dose limiting toxicity is observed up to and including at the 40 mg/kg dose. If dose escalation above 40 mg/kg is feasible based on the above criteria, these higher doses may be investigated in additional SAD and MAD cohorts in healthy subjects and in subjects with CG or GALK-deficient Galactosemia if no AT-007 levels are detected in the CSF collected from the healthy subjects enrolled in Cohort C3.

All doses of study drug (AT-007 or placebo) should be taken in the morning under fasting conditions (after at least a 10-hour overnight fast that is broken 2 hours after dosing [mandatory for doses with PK sampling time points and recommended for all other doses]). This will be the case regardless of whether the study drug dose is taken at the CRU or at home.

